3.3 Treatment

Baseline Phase:

During the baseline phase, patients who sign an informed consent form will undergo initial screening. On the final day of the baseline phase, patients' eligibility will be determined, based on inclusion/exclusion criteria, and qualified patients will enter the treatment phase.

Treatment Phase:

At the beginning of the treatment phase, patients will be randomized in a 2:1 ratio to receive either deferiprone or deferoxamine. The treatment phase will be 52 weeks in duration.

Deferiprone Treatment Arm:

Patients will be prescribed Ferriprox 500 mg tablets and/or 80 mg/mL oral solution, according to patient preference or product's availability, for administration three times a day (tid). The dose of Ferriprox will be based on the transfusional iron input and the severity of iron overload at baseline, and may be adjusted on the basis of the magnitude of change in iron overload during the study.

Ferriprox 25 mg/kg tid:

Patients with transfusional iron input ≤ 0.3 mg/kg/day in the 3 months prior to baseline

AND

Patients with a baseline measure of iron load of:

- Serum ferritin < 2500 $\mu\text{g/L}$

AND

- LIC < 15 mg/g dry weight

AND

- Cardiac T2* > 20 ms

Ferriprox 33 mg/kg tid:

Patients with a transfusional iron input > 0.3 mg/kg/day in the 3 months prior to baseline

OR

Patients with at least one baseline measure of iron load as follows:

- Serum ferritin ≥ 2500 $\mu\text{g/L}$

OR

- LIC ≥ 15 mg/g dry weight

OR

- Cardiac T2* ≤ 20 ms

Dosing of all patients will be initially at 15 mg/kg tid for 1 week, which will be increased to 20 mg/kg tid in Week 2 and to 25 mg/kg tid in Week 3, which will be the treatment dose for the remainder of the trial, unless a patient meets the 33 mg/kg tid dosing criteria. In that case, the dose of Ferriprox will be increased further to 33 mg/kg tid in Week 4, and this dose will be the treatment dose for the remainder of the trial.

The dose of Ferriprox will also be increased to 33 mg/kg tid at any time during the trial if the mean daily transfusional iron input increases to more than 0.3 mg/kg body weight for at least 3 consecutive months OR at Week 26 if there is less than 10% improvement from baseline to Week 26 in at least one of the measures indicative of iron overload (serum ferritin, cardiac MRI T2* or LIC).

Dose reduction recommendations will be based on regular assessment of safety markers for adverse reactions that are possibly dose dependent, such as gastrointestinal upset, increases in serum liver enzyme levels, and arthropathies.

Deferoxamine Treatment Arm:

Patients will be prescribed deferoxamine as per the approved US prescribing information at doses of 20 – 40 mg/kg/day for children (<16 years of age) and 40–50 mg/kg/day in adults (≥ 16 years of age) as 8 – 12 h subcutaneous infusion for 5 – 7 days per week. The dose of deferoxamine will be based on the transfusional iron input, on the severity of iron overload at baseline, and on the magnitude of its change during the study.

Deferoxamine 20 mg/kg/day (children) or 40 mg/kg/day (adults):

Patients with transfusional iron input ≤ 0.3 mg/kg/day in the 3 months prior to baseline

AND

Patients with a baseline measure of iron load of:

- Serum ferritin < 2500 $\mu\text{g/L}$

AND

- LIC < 15 mg/g dry weight

AND

- Cardiac T2 > 20 ms

Deferoxamine up to 40 mg/kg/day (children) or 50 mg/kg/day (adults):

Patients with a transfusional iron input > 0.3 mg/kg/day in the 3 months prior to baseline

OR

Patients with at least one baseline measure of iron load as follows:

- Serum ferritin ≥ 2500 $\mu\text{g/L}$

OR

- LIC ≥ 15 mg/g dry weight

OR

- Cardiac T2* ≤ 20 ms

Children (<16 years of age).

The dose of deferoxamine will also be increased up to 40 mg/kg for 5 – 7 days per week at any time during the trial if the mean daily transfusional iron input increases to more than 0.3 mg/kg body weight for at least 3 consecutive months OR at Week 26 if there is less than 10% improvement from baseline to Week 26 in at least one of the measures of iron overload (serum ferritin, cardiac MRI T2* or LIC).

Adults (≥ 16 years of age)

The dose of deferoxamine will be increased up to 50 mg/kg for 5 – 7 days per week at any time during the trial if the mean daily transfusional iron input increases to more than 0.3 mg/kg body weight for at least 3 consecutive months OR at Week 26 if there is less than 10% improvement from baseline to Week 26 in at least one of the measures of iron overload (serum ferritin, cardiac MRI T2* or LIC).

Dose reduction recommendations will be based on regular assessment of safety markers. Efficacy, safety and tolerability evaluations will occur according to the schedule of evaluation (Table 1). Rescue medication (intravenous administration of deferoxamine or combination of 2 iron chelators: Ferriprox, deferoxamine or deferasirox) for the treatment of iron overload will not be allowed during the Treatment Phase. Should iron overload symptoms become intolerable for the patient despite dose adjustment, the Investigator should withdraw the patient from the study.

If a patient withdraws early, he or she will return to the clinic for an Early Termination Visit as soon as possible, and no later than 1 month following treatment discontinuation.

All of the efficacy and safety evaluations will be performed at the last study visit or the Early Termination visit, whichever comes first.

3.4 Study Sites and Study Duration

Study sites have been located in USA, Canada, Brazil, United Kingdom, Egypt, Saudi Arabia, Tunisia, and Turkey. Each patient is expected to participate in the study for approximately 60 weeks (from the Screening Visit to the End of Study Visit).

3.5 Schedule of Study Procedures

The efficacy and safety measurements/evaluations will be performed at visits outlined in Table 1 – Schedule of Study Procedures.

Table 1. Schedule of Study Procedures

STUDY PROCEDURE	Baseline Phase				Treatment Phase			
	Screening/ Baseline	Baseline	Hematology Assessments ¹	Telephone Calls (Week 1, 2, 3)	Monthly Visits (Week 4, 8, 16, 20, 32, 36, 44, 48)	Quarterly Visits (Week 12, 40)	Semi-Annual Visit (Week 26)	End of Study / Early Termination Visit ² (Week 52)
Informed Consent/Assent	X							
Eligibility Criteria	X							
Previous/current chelation therapy	X							
Confirmation of eligibility		X						
Demographic	X							
Randomization		X						
Medical history	X	V						R
Transfusion history	X	X						
Prior and Current medications	X	V						X
Hematology	X ³	X ⁴	X		X	X	X	X
Biochemistry	X ^{3,4}	V			X	X	X	X
Serum Pregnancy testing (females of childbearing potential only)	X ³	X			X	X	X	X
Urine Pregnancy testing (females of childbearing potential only)		X						
Serology	X ^{3,4}	V					X	X
Urinalysis	X ^{3,4}	V					X	X
Physical examination	X ^{3,4}	V					X	X
Vital signs (including weight and height) ⁵	X	X ⁴			X	X	X	X
12-lead ECG	X ^{3,4}	V					X	X
Blood sample for genetic polymorphism of agranulocytosis (optional)		X						

STUDY PROCEDURE	Baseline Phase			Treatment Phase				
	Screening/ Baseline	Baseline	Hematology Assessments ¹	Telephone Calls (Week 1, 2, 3)	Monthly Visits (Week 4, 8, 16, 20, 32, 36, 44, 48)	Quarterly Visits (Week 12, 40)	Semi-Annual Visit (Week 26)	End of Study / Early Termination Visit ² (Week 52)
Contraceptive counselling	X	X			X	X	X	
Quality of Life Questionnaire (SF-36/ Child Health Questionnaire)		X					X	X
Serum Ferritin		X				X	X	X
Liver MRI/LIC	X ^{4,6}						X	X
Cardiac MRI T2*	X ^{4,6}						X	X
Dose Calculation/Verify and adjust dose level		X			X	X	X	
Contact IVRS/IWRS		X			X	X	X	X
Dispense study medication		X			X	X	X	
Dispense Patient Diary Card		X			X	X	X	
Review and Collect Diary Card					X	X	X	X
Medical events/Adverse events	X	X		X	X	X	X	X
Concomitant medications				X	X	X	X	X
Transfusion information (if applicable) ⁷			X		X	X	X	X
Return used and unused study medication					X	X	X	X

X- To do, V- To verify, R- To review

1. Hematology testing is to be done weekly up to Week 26 and biweekly thereafter.
2. Early Termination: if patient withdraws from the study prior to Week 52, the patient must be seen for an early termination visit.
3. These evaluations must be done within 14 days prior to baseline visit. Females of childbearing potential must be making use of an approved birth control method at least one month prior to starting study medication.
4. Results from these tests will be considered the baseline values.
5. Height will only be measured at screening/baseline, semi-annual and Week 52 visits.
6. These evaluations must be conducted within two months prior to starting study medication
7. Collect volume of blood that the patient received during the transfusion and the mean hematocrit of the packed red blood cell units transfused.

3.6 Method of Assignment to Treatment

At the baseline visit, patients will be randomly assigned to receive Ferriprox or deferoxamine in a 2:1 ratio. Stratified randomization based on disease category (sickle cell disease vs. other anemias) and on the transfusional iron input in the 3 months prior to baseline (> 0.3 mg/kg/day vs. ≤ 0.3 mg/kg/day) will be employed to ensure that the 2:1 ratio is maintained within each of the 4 strata: 1) sickle cell disease with transfusional iron input > 0.3 mg/kg/day, 2) sickle cell disease with transfusional iron input ≤ 0.3 mg/kg/day, 3) other anemias with transfusional iron input > 0.3 mg/kg/day, and 4) other anemias with transfusional iron input ≤ 0.3 mg/kg/day. Treatment assignment and drug allocation will be performed by an Interactive Voice Response System (IVRS).

3.7 Interim Analysis

An interim analysis will be performed with the data of patients who will have either completed or been withdrawn from the study by November 30, 2018. The Pocock's α spending function (Lan and DeMets, Discrete sequential boundaries for clinical trials. Biometrika, 1983; 70:659-663) will be used for assigning α for this interim analysis. The Pocock's α spending function is:

$$\alpha(t) = \alpha \times \ln [1 + (e - 1) \times t]$$

where $\alpha = 0.05$ and $t = \text{information fraction}$

$$\begin{aligned} &= \text{number of patients at the interim analysis / total number of patients} \\ &= 213 \text{ patients / 300 patients} \\ &= 0.71 \end{aligned}$$

Substituting the values of $\alpha = 0.05$, $t = 0.71$, and $e = 2.718$ into the Pocock's α spending function gives

$$\alpha(t) = 0.05 \times \ln [1 + (2.718 - 1) \times 0.71]$$

$$= 0.05 \times \ln [2.21978]$$

$$= 0.0399$$

Therefore, $\alpha = 0.0399$ will be used for the interim analysis.

A study report will be prepared with the results of the interim analysis and the decision to re-start patient enrollment will be based on the advice of the Data and Safety Monitoring Board (DSMB) after their review of the interim analysis results.

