**Schedule of Study Procedures:**

Following screening assessments, eligible patients will undergo baseline assessments within two months of the screening assessments.

1. MRI scans will be performed at Screening/Baseline, and Weeks 26 and 52 (End of Study) or Early Termination visits, whichever comes first for:
  - Liver MRI for LIC calculation;
  - Cardiac MRI T2\* ;
2. Serum ferritin will be measured at Baseline and Weeks 12, 26, 40 and 52 (End of Study) or Early Termination visits, whichever comes first;
3. Hematology assessments will be performed at Screening/Baseline, weekly until Week 26, and then biweekly until Week 52 (End of Study) or Early Termination visits, whichever comes first;
4. Chemistry assessments will be performed at Screening/Baseline, and monthly up to Week 52 (End of Study) or Early Termination visits, whichever comes first.
5. Quality of life patient-reported questionnaire will be completed at Baseline and Weeks 26 and 52 (End of Study) or Early Termination visits, whichever comes first.

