However, patient's recruitment in this study has proceeded at a very slow pace and despite all our efforts over the past 4 years, the goal of enrolling a total of 300 patients has not been reached. A total of 213 patients (142 patients for Ferriprox and 71 patients for deferoxamine) are projected to have either completed the study or been withdrawn from the study by November 30, 2018. An interim analysis is planned to be performed on the data of these 213 patients. Based on the same values of non-inferiority margin and SD of the LIC measurement, but an α level of 0.0399, two-sided (Pocock's α spending method, see section 3.7 for details), this sample size (213 patients) will provide 89% power to demonstrate non-inferiority of Ferriprox to deferoxamine in this interim analysis, assuming no real difference in efficacy between the two treatments. For the subgroup analysis of only patients with sickle cell disease, the power will be 82% as there are 178 SCD patients (119 patients for Ferriprox and 59 patients for deferoxamine), which is approximately 84% of 213 patients. With the safety data of 213 patients, there is 98% chance (power) of occurrence of at least 1 SAE with an anticipated incidence rate of 2%, or 88% chance for an anticipated incidence rate of as low as 1%.

During this interim analysis, while patient enrollment has been put on hold, there will still be 17 patients who are on-going with their assigned drug treatment. All are projected to have completed the study by October, 2019. If the results of the interim analysis lead to the conclusion of non-inferiority of Ferriprox to deferoxamine, considerations will be given on early termination of the study, to avoid unnecessary exposure of patients to a clinical trial that has reached its objectives. The data from those patients up to the time of

study closure will be added to the interim dataset for the final statistical analysis of the study based on the same statistical analyses in this SAP.

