4.1 Intent-to-Treat Population

The ITT population will include all randomized patients who received at least one dose of study drug and have a baseline and at least one post-baseline efficacy assessment. There can be a different number of patients (N) in the ITT population for each of the four efficacy measures (LIC, serum ferritin, cardiac T2*, and quality of life) if some of the patients don't have post-baseline data on all of the three efficacy measures. All efficacy analyses will be based on the ITT population.

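### The interim efficacy set is defined by disposition, so patients randomised less than 52 weeks before the cut-off enter the non-inferiority test only if they withdrew; define it by randomisation date instead

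*SAP*

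**What the plan says.** SAP 3.7 takes as its interim data set "patients who will have either completed or been withdrawn from the study by November 30, 2018". The SAP's sample size section gives the count: "A total of 213 patients (142 patients for Ferriprox and 71 patients for deferoxamine) are projected to have either completed" or withdrawn by that date. The same section adds that "there will still be 17 patients who are on-going with their assigned drug treatment" and that "All are projected to have completed the study by October, 2019". If the study closes early, the data of these patients up to "study closure will be added to the interim dataset for the final statistical analysis of the study".

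Three other provisions bear on this:

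- **Duration.** SAP 3.3: "The treatment phase will be 52 weeks in duration".
- **LIC timing.** Protocol synopsis, Schedule of Study Procedures: "MRI scans will be performed at Screening/Baseline, and Weeks 26 and 52 (End of Study) or Early Termination visits". Week 26 is therefore the first scheduled post-baseline LIC for a patient who stays on treatment.
- **ITT definition.** SAP 4.1 admits "all randomized patients who received at least one dose of study drug and have a baseline and at least one post-baseline efficacy assessment". Neither completion nor withdrawal is required. The primary mixed model in 7.1 uses Month 6 as well as Month 12.

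An ongoing patient with a Week 26 scan meets the 4.1 definition and fits the 7.1 model, but 3.7 leaves that patient out. The SAP does not reconcile the two.

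**The concern.** Among patients with less than 52 weeks of possible follow-up, 3.7 takes those who withdrew and leaves out those who stayed. That is selection on a post-randomisation event. The trial is open-label and compares an oral drug with subcutaneous infusions of 8–12 hours, so the rate of withdrawal and the reasons for it may differ between arms. Under SAP Section 5, withdrawn patients whose last measure lies outside the 30-day window get a carried-forward or worst-in-arm value, so the selected patients bring mostly imputed Week 52 data.

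The interim is a formal non-inferiority test at two-sided alpha 0.0399. According to the sample size section, a positive result leads to early termination being considered. The data set behind such a test should not depend on who happened to drop out.

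**Working it through.** **1. The plan's own figure.** SAP 3.7 uses α(t) = 0.05 × ln[1 + (e − 1)t] with t = 213/300 = 0.71. This gives 0.05 × ln(2.220) = 0.0399, as stated.

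**2. Dates.**
- 30 November 2018 minus 52 weeks is 1 December 2017. A later entrant cannot be a completer, apart from the ±7-day window in protocol 5.9.
- 30 November 2018 minus 26 weeks is 1 June 2018. A later entrant still on treatment has not reached the Week 26 scan, again apart from the window.
- Last completion in October 2019 minus 52 weeks puts the last entry between 2 October and 1 November 2018. The latest of the 17 cannot have a post-baseline LIC.
- If the 17 entered evenly from 1 December 2017 (assumed), those past Week 26 number 17 × 182/335 = 9.2 to 17 × 182/305 = 10.1. The documents give no count.
- Share held back: 17/(213 + 17) = 7.4%.

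**3. Recent withdrawals in the 213.** Assume even entry over the last 52 weeks and exponential drop-out with 12-month rate d, and put λ = −ln(1 − d). The fraction of recent enrolees withdrawn by the cut-off is f = 1 − d/λ. Recent withdrawals are w = 17/(1 − f) − 17. The excess drop-out share in the interim set is w(1 − d)/213.

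| d | f | w | excess (percentage points) |
|---|---|---|---|
| 10% | 5.1% | 0.9 | 0.4 |
| 20% | 10.4% | 2.0 | 0.7 |
| 30% | 15.9% | 3.2 | 1.1 |
| 40% | 21.7% | 4.7 | 1.3 |

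These counts are upper limits, because 4.1 also requires a post-baseline LIC.

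**4. Shift in the treatment difference (Ferriprox minus deferoxamine).** Shift = gap × (excess in Ferriprox − excess in deferoxamine). The gap is how much worse (higher) the LIC change is in withdrawn than in completing patients. Each arm's excess is its own w(1 − d)/N, with N = 142 or 71. Drop-out rates, gaps and the split of the 17 are all assumptions.

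- Equal drop-out, 17 split 2:1: the excesses are equal, so the shift is 0.
- 30% Ferriprox, 10% deferoxamine, 2:1 split, gap 4: (2.14 × 0.7/142 − 0.30 × 0.9/71) × 4 = (1.06% − 0.39%) × 4 = 0.03 mg/g. With the rates swapped it is −0.03.
- 40% and 10%, 2:1 split, gap 14: (1.33% − 0.39%) × 14 = 0.13.
- 10% and 30%, 17 split 5:12, gap 14: (0.17% − 2.24%) × 14 = −0.29.

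A negative shift favours a finding of non-inferiority. With SD 4, the standard error of the difference is 4 × √(1/142 + 1/71) = 0.58. The margin is 2.

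**5. Effect of a randomisation-date rule.** Removing 1 to 5 patients leaves 212 to 208, so t = 0.707 to 0.693 and alpha = 0.0397 to 0.0392. Power by non-central t (margin 2, SD 4, 2:1) is 91.3% to 90.7%, against 91.4% for 142:71 at 0.0399. The SAP states 89% for that last case. The gap to 91.4% is a separate matter, and the comparison here uses one method throughout.

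**The case against.** The case for leaving 3.7 alone is substantial.

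- Waiting until each patient's Week 52 outcome is settled is a common administrative cut-off, and none of the 17 has reached the primary time point.
- The data of the 17 are deferred, not lost.
- The per-protocol LIC analysis (4.2) takes completers only, so recent withdrawals cannot enter it.
- SAP 7.5 repeats the primary analysis in patients with at least 6 months of LIC data. It also runs a stress test against Ferriprox, with worst values for its drop-outs and carried-forward values for those on deferoxamine.
- Early termination is only to be considered, and re-starting enrolment depends on DSMB advice.

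All of this stands, and it limits the size of the problem. It does not remove it. The per-protocol and 6-month analyses also drop withdrawals among patients with full potential follow-up, and the 6-month analysis keeps recent withdrawals who have a Week 26 scan. The stress test runs on the same selected cohort. None of them corrects the primary test.

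Three stronger readings are tempting, and the documents do not support them. One is that patients are chosen by outcome: the rule uses completion or withdrawal, not LIC. Another is that usable data from 17 patients are thrown away: the number with a post-baseline LIC is not given, the latest entrants cannot have one, and the sample size section brings these patients into the final analysis. The third is that the selection could plausibly decide the result: the shifts in moderate scenarios are far too small.

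**Conclusion.** The selection is real and follows from the wording of 3.7 and the 52-week treatment period alone. Its likely effect is minor: at most about 1–5 of 213 patients, and a shift between 0 and about 0.03 mg/g dw in either direction in moderate scenarios, roughly one-twentieth of a standard error. Shifts of 0.13–0.29 need a 14 mg/g gap together with very unequal drop-out or a very uneven split of the 17, and nothing in the documents points to either. Even 0.29 is about half a standard error and about one-seventh of the margin. All these sizes rest on assumed drop-out, entry dates and arm split, because the documents give none of them. The reason to act is that a test which may lead to early closure should have a data set that withdrawal cannot influence, and that this is easily arranged.

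**What to change.** In SAP 3.7, define the interim efficacy set as all patients randomised at least 52 weeks before 30 November 2018, whatever their disposition. State how a Week 52 visit that falls within its 7-day window but after the cut-off is handled. Recompute the information fraction and alpha from the resulting count, and say in 3.7 that the ITT definition of 4.1 is applied within this set.

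As a sensitivity analysis, add to the mixed model every LIC obtained by the cut-off from later-randomised patients. Visits not yet due should not be imputed, so the carry-forward rule in Section 5 must not be applied to them. The information fraction should not rise. Counting all 230 patients would give t = 230/300 = 0.767 and alpha 0.0420, which credits full information to patients without a Week 52 LIC.

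The cost is a few sentences in the SAP. A few recent withdrawals leave the 213, alpha falls from 0.0399 to about 0.0392–0.0397, and power falls by less than one percentage point under the assumptions above. Label: cheap improvement.

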#### **11.4.1.3 Efficacy Analyses**

##### **Primary Efficacy Endpoint**

The change from baseline to Week 52 in LIC will be compared between the two treatment groups using an analysis of covariance (ANCOVA) model, including treatment variable as the main factor and total transfusional iron input during the study and baseline LIC as covariates. The 95% confidence interval (CI) of the difference (deferiprone minus deferoxamine) in change of LIC from baseline to Week 52 between the two treatment groups will be computed. For the demonstration of non-inferiority, the upper limit of the 95% CI should be no more than 2 mg/g dw.

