7.1 Primary Efficacy Endpoint

Primary efficacy endpoint is the change from baseline to Week 52 in LIC. Primary efficacy endpoint will be compared between the two treatment groups using an analysis of covariance (ANCOVA) model including treatment variable as the main factor, and overall average transfusional iron input during the study, baseline LIC, and stratification factors (disease category and transfusional iron input in the 3 months prior to baseline) as covariates. The 96.01% $(1 - \alpha)$, where $\alpha = 0.0399$ based on the Pocock’s α spending function for interim analysis) confidence interval (CI) of the difference (Ferriprox minus deferoxamine) in change of LIC from baseline to Week 52 (i.e., Week 52 minus baseline) between the two treatment groups

will be computed. For the demonstration of non-inferiority, the upper limit of the 96.01% CI should be no more than 2 mg/g dw.

The following SAS codes of MIXED procedure will be used to produce the differences in Least Squares (LS) Mean of change in LIC at Month 6 and Month 12 between Ferriprox and deferoxamine groups and the corresponding 96.01% confidence intervals. In the mixed model, AR (1) (autoregressive of order 1) will be used for the covariance structure, and Kenward and Roger's method will be used to estimate the denominator degrees of freedom (SAS model statement option, DDFM = KR).

```

proc mixed data=LIC;
  class patient treat disease prior_iron month
  model LIC_change = treat overall_iron base_LIC disease prior_iron
    month treat*month / noint solution ddfm=kr;
  repeated month / subject=patient(treat) type=ar(1);
  lsmeans treat*month;
  estimate 'Ferriprox - Deferoxamine at Month 6' treat -1 1
    treat*month -1 0 1 0 / cl alpha=0.0399;
  estimate 'Ferriprox - Deferoxamine at Month 12' treat -1 1
    treat*month 0 -1 0 1 / cl alpha=0.0399;
run;

```

Definition of the variables in the statistical model:

LIC_change : Change in LIC from baseline to Week 5
 treat : Ferriprox or Deferoxamine
 month : Duration of treatment in month
 overall_iron : Overall total transfusional iron input (mg/kg/day) during the study
 base_LIC : LIC at baseline
 disease : Sickle cell disease or other anemias
 prior_iron : transfusional iron input in 3 months prior to baseline (≤ 0.3 mg/kg/day or > 0.3 mg/kg/day)

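### SAP 3.7 lets enrolment restart after a missed interim but gives no level for the final analysis; reusing the interim 96.01% CI at 300 patients would give a one-sided error of 0.0303 against 0.025

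*SAP*

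**What the plan says.** **Interim level.** SAP 3.7 applies a Pocock-type spending function with total two-sided alpha 0.05. The information fraction is defined as "number of patients at the interim analysis / total number of patients", which is 213/300 = 0.71. The resulting 0.0399 "will be used for the interim analysis".

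**After the interim.** SAP 3.7 ends with the restart provision: "the decision to re-start patient enrollment will be based on the advice of the Data and Safety Monitoring Board (DSMB", after the board has reviewed the interim results. The SAP's sample size text, just before section 3.3, covers other outcomes. Enrolment is on hold, but "there will still be 17 patients who are on-going with their assigned drug treatment", so at most 213 + 17 = 230 patients contribute without a restart. If the interim shows non-inferiority, early termination will be considered "to avoid unnecessary exposure of patients to a clinical trial that has reached its objectives". The data accrued up to closure are then added for a final analysis by the same methods.

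**Success criteria in print.** There are two:
- SAP 7.1: "For the demonstration of non-inferiority, the upper limit of the 96.01% CI should be no more than 2 mg/g dw". The same section explains that 96.01% comes from the interim spending calculation. The level is fixed in the SAS code (Month 12 estimate: "treat*month 0 -1 0 1 / cl alpha=0.0399") and in the column heading of table shell 14.2.1.3.
- Protocol 11.4.1.3: "For the demonstration of non-inferiority, the upper limit of the 95% CI should be no more than 2 mg/g dw". The protocol's statistical section plans no efficacy interim.

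Neither document gives an alpha, critical value or CI level for an analysis after a missed interim and a restart.

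**The concern.** A two-look design controls type I error only if both boundaries are set. Here the first is set and the second is not, although the plan expressly allows the trial to reach it. An analyst at the 300-patient stage would find one criterion in the SAP, one in the SAS program and one in the table shells, all at 96.01%. That level uses as much nominal alpha at the second look as at the first, although most of the total had already been spent. The protocol describes the trial as a confirmatory commitment following accelerated approval, so the error rate of its non-inferiority claim will be examined. A level first written down after the interim results are known is harder to defend than one printed beforehand, even if it can be derived.

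**Working it through.** **Inputs.** Total alpha 0.05 two-sided, or 0.025 one-sided (Protocol 11.2.4 and SAP sample size text). Interim at 213 patients, 142 and 71, and planned total 300 (SAP sample size text and 3.7). Margin 2 mg/g dw, SD 4.0 in both arms, true difference 0 (same text). Final allocation at 300 is 200 and 100, from the 2:1 ratio.

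**Step 1: reproduce the SAP's figure.** 0.05 × ln[1 + 1.718 × 0.71] = 0.05 × ln(2.21978) = 0.0399. This agrees with SAP 3.7. One-sided it is 0.01995, so the interim bound is z = 2.055. The unspent one-sided alpha is 0.025 − 0.01995 = 0.00505.

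**Step 2: overall error if a printed criterion is reused.** Under the null, the two test statistics are treated as bivariate normal with correlation √(213/N). The overall one-sided error is

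1 − P(Z₁ < 2.055, Z₂ < c),

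where c is the critical value at the final look.

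| Final N | Correlation | c = 2.055 (96.01% CI) | c = 1.960 (95% CI) |
|---|---|---|---|
| 300 | √0.71 = 0.843 | 0.0303 | 0.0341 |
| 230 | √0.926 = 0.962 | 0.0252 | 0.0286 |

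A simulation of 20 million draws gave 0.0303 and 0.0341 at 300. Reusing 96.01% at 300 adds 0.0303 − 0.01995 = 0.01035, about twice the 0.00505 that remained. The total is 0.0303/0.025 = 1.21 times the planned error.

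**Step 3: the level that holds 0.025 at 300.** Solving 1 − P(Z₁ < 2.055, Z₂ < c) = 0.025 with correlation 0.843 gives c = 2.254. That is 0.0121 one-sided, 0.0242 two-sided, or a 97.58% CI. It exceeds the unspent two-sided 0.0101 because the two looks share data.

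**Step 4: power (normal approximation).** The expected test statistic is 2/(4√(1/142 + 1/71)) = 3.44 at the interim and 2/(4√(1/200 + 1/100)) = 4.08 at 300.
- Interim power: 91.7%. The SAP states 89%, which these inputs do not reproduce.
- Overall power over both looks: 98.2% with the final at 0.0399, and 97.4% with the final at 0.0242.
- Power given a missed interim: (98.2 − 91.7)/(100 − 91.7), about 78%, and (97.4 − 91.7)/(100 − 91.7), about 68%. The unrounded calculation gives 78.1% and 68.1%.

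**The case against.** The strongest reply is that the plan already determines the answer. SAP 3.7 gives the total alpha, a named spending function with its formula, and a denominator of 300. Under that function cumulative alpha at full information is 0.05, so 0.0242 can be computed before any result is seen. This largely stands: the level is not an open choice for anyone who continues the same function. But SAP 3.7 invokes the function only for this interim, and the resulting level is printed nowhere. The criterion, code and shells that are printed carry a different one.

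A second reply is that the SAP never tells anyone to use 96.01% at 300. That is correct. A reader might infer from SAP 7.1 and the fixed SAS code that 96.01% is the prescribed final criterion, but 3.7 and 7.1 both tie it to the interim. The 0.0303 is therefore what would follow from reuse, not the error rate of a stated rule. The 0.0341 case is weaker still, because the SAP replaced the protocol's 95% level.

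A third reply is that the path is narrow. This also stands. Material inflation needs a missed interim, a restart well beyond 230 patients, and the wrong criterion at the end. Under the SAP's own assumptions a missed interim has a probability of 11% (8.3% by the calculation above).

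Finally, part of the SAP before the sample size text is not readable in the public copy. Sections 3.7 and 7.1, where the level belongs, are readable.

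**Conclusion.** The point holds for the restart path only. The plan foresees an analysis after a missed interim and does not state its level, and the SAP's one printed criterion would give an overall one-sided error of 0.0303 instead of 0.025 if reused at 300.

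A reader might conclude that the design inflates type I error in general. The documents do not support that. If the interim misses and only the 17 ongoing patients are added, reuse of 96.01% gives 0.0252, which is negligible. If the interim succeeds, non-inferiority has already been declared at the interim boundary, and the later enlarged analysis adds no error.

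The figures assume information proportional to patient count, independent increments, exactly 213 patients at the interim (a projected number in the SAP), and success declared if either look meets its criterion. This should be fixed before the interim results are seen.

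**What to change.** Add one rule to SAP 3.7 and repeat it in 7.1: if the interim does not show non-inferiority and enrolment restarts to the planned 300, the final analysis is tested at the level that brings cumulative two-sided alpha to 0.05 under the same spending function, recomputed from the actual number of patients in the interim. Give the worked example: with 213 of 300, two-sided 0.0242, so the upper limit of the 97.58% CI must be no more than 2 mg/g dw. Replace the fixed 0.0399 in the SAS code, and the fixed 96.01% in the table shells, with a CI-level parameter set for each analysis.

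The drafting cost is a few sentences and one program parameter. The statistical cost, compared with reusing 0.0399 at 300, is overall power of about 97.4% instead of 98.2%. On the path concerned, power given a missed interim is about 68% instead of 78%. These use the normal approximation with SD 4, margin 2 and true difference 0, and an interim power of 91.7% where the SAP states 89%. The absolute values would shift if the SAP's figure reflects an allowance that it does not describe.
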